4.5 Device Accountability

The FARAPULSE Cardiac Ablation System will be housed in a secure location and access will be controlled. Records will be maintained to document the physical location of inventory from shipment and removal from Sponsor facility through use and/ or return or disposal.

The site will be responsible for keeping a Device Accountability Log provided by the Sponsor or its designated representative in which will be recorded, at a minimum, date of receipt, FARAPULSE Cardiac Ablation System identification number, expiration date, date of use, subject unique identity code and date of disposal of the device.

If there is a product malfunction or other need to return the system or system components to the Sponsor, the Sponsor should be contacted for safe product disposal and/ or return details.

The Investigator is responsible for ensuring that the investigational devices are used only under the Investigator's supervision and are only used according to this protocol and any approved amendments. The Investigator will not supply an investigational device to any person not authorized to participate in the study. The Investigator shall document in the Case Report Forms (CRFs) the lot numbers of the devices used during each case.

4.6 Return of Devices

All unused investigational devices will be returned to the study Sponsor upon completion of the clinical study. All used investigational devices will be returned to the study Sponsor for analysis. Any investigational device that fails to perform correctly will be equally returned to the study Sponsor for analysis. The Investigator or his/ her designated representative is responsible for device accountability and disposition of all used and unused devices. The study Sponsor or its designated representative will conduct device reconciliation at the completion of subject enrollment or at the conclusion of the study.

5. Trial Objectives

The objective of this feasibility and safety trial is to demonstrate that the creation of electrically isolating lesions generated by pulsed electric field ablation using the FARAPULSE Cardiac Ablation System during concomitant heart surgery is feasible and a safe treatment for paroxysmal atrial fibrillation.

5.1 Study design

The IMPACT Study is a prospective, observational, multi-center, intention-to-treat study using the FARAPULSE Cardiac Ablation System in subjects with paroxysmal atrial fibrillation who consented to undergo surgical PEF ablation concomitant to heart surgery.

5.2 Selection and Withdrawal of Subjects

5.2.1 Inclusion Criteria

All subjects are required to meet all of the following inclusion criteria in order to be considered eligible for participation in this trial:

- 1. Patients who are \geq 18 and \leq 70 years of age on the day of enrollment.
- 2. Diagnosis of paroxysmal atrial fibrillation defined as symptomatic paroxysmal AF with at least two episodes of paroxysmal AF observed within the 12 months preceding inclusion.
- 3. Patients are resistant to anti-arrhythmic treatments.
- Anteroposterior Left atrial diameter ≤ 5.5 cm as documented by transthoracic echocardiography (TTE) or computed tomography (CT) within 3 months prior to the procedure.
- 5. Subject has no contraindications to intraoperative transesophageal echocardiography;
- 6. Subject is scheduled to undergo elective on-pump cardiac surgical procedure(s) to be performed including open-heart surgery for one or more of the following:
- Mitral valve repair or replacement,
- Aortic valve repair or replacement
- · Tricuspid valve repair or replacement, or
- Coronary artery bypass procedures
- 7. Left ventricular ejection fraction ≥40% as documented by TTE within 12 months prior to the procedure.
- 8. Received a standard cardiac work up and is an appropriate candidate for an investigational procedure as determined by trial investigators.

9. Subject is willing and capable of providing Informed Consent to undergo study procedures and participate in all examinations and follow-ups associated with this clinical trial.

5.2.2 Exclusion Criteria

Subjects will be excluded from participating in this trial if they meet any of the following exclusion criteria:

- Abnormal cardiac and/or epicardial anatomy (such as adhesion, anomalous coronaries, thickened epicardium, etc.) or pericardial reflections on TTE, MRI or CT.
- 2. Prior left-sided cardiac ablation.
- 3. Prior history of open chest surgery and/or any procedure where the pericardial space was entered or instrumented (pericardiocentesis, catheter mapping and /or ablation).
- 4. Patient has a prosthetic heart valve.
- 5. Patient has a left atrial appendage device
- 6. Prior history of pericarditis or pericarditis within 3 months based on the TTE examination.
- 7. Subject is a woman of child bearing age
- 8. Prior history of rheumatic fever.
- 9. Prior history of medical procedure involving instrumentation of the left atrium (previous ablation, Atrial septal defect) ASD closure, left atrial appendage occlusion)
- 10. History of severe chronic gastrointenstinal problems involving the esophagus, stomach and/or untreated acid reflux
- 11. History of abnormal bleeding and/or clotting disorder.
- 12. Active malignancy or history of treated cancer within 24 months of enrollment.
- 13. Clinically significant infection or sepsis.
- 14. History of stroke or TIA within prior 6 months
- 15. New York heart Association (NYHA) class IIIb or IV congestive heart failure and/or any heart failure hospitalization within 3 months prior to enrollment.
- 16. Body mass index > 35.
- 17. Estimate glomerular filtration rate (eGFR) < 60 mL/min/1.73 m2 or has ever received dialysis.
- 18. History of untreated and serious hypotension, bradycardia or chronotropic incompetence.
- 19. Any of the following within 3 months of enrollment
 - Major surgery except for the index procedure
 - Myocardial infarction
 - Unstable angina
 - Percutaneous coronary intervention (e.g., CABG or PTCA)
 - Sudden cardiac death event

- Left atrial thrombus that has not resolved as shown by TEE or CT
- Implant of pacemaker, ICD or CRT.
- 20. Solid organ or hematologic transplant, or currently being evaluated for an organ transplant
- 21. History of pulmonary hypertension with Pulmonary systolic artery pressure >50 mm Hg, severe Chronic Obstructive Pulmonary Disease or restrictive lung disease.
- 22. Patients with any other significant uncontrolled or unstable medical condition (such as uncontrolled brady-arrhythmias, ventricular arrhythmias, hyperthyroidism or significant coagulation disorder).
- 23. Life expectancy less than one year.
- 24. Clinically significant psychological condition that in the physician's opinion would prohibit the subject's ability to meet the protocol requirements.
- 25. Enrolled in another cardiac clinical trial that would interfere with this trial.
- 26. Life expectancy less than one year.
- 27. Clinically significant psychological condition that in the physician's opinion would prohibit the subject's ability to meet the protocol requirements.
- 28. Enrolled in another cardiac clinical trial that would interfere with this trial.

5.3 Trial Design

5.3.1 Description of Trial Design

Prospective, single-arm, multi-center feasibility trial. Subjects will be consented to undergo surgical PEF ablation using the FARAPULSE Cardiac Ablation System concomitant to heart surgery. Subjects will be followed at 30 days, 3 months, 6 months and 12 months following the index surgical procedure with a blanking period for recurrent atrial fibrillation or atrial tachycardia of 3 months following the index surgical procedure.

5.4 Trial Endpoints

5.4.1 Primary Safety Endpoint

A composite safety endpoint consisting of the proportion of subjects that experience one or more of the following serious adverse events (SAEs) related to the investigational procedure and/or device within 30 days of the PEF ablation procedure or hospital discharge, whichever is later, except as noted below:

- Cardiac death
- Stroke and/or transient ischemic attack (TIA)

- Myocardial infarction (MI)
- Excessive bleeding
- Atrio-esophageal fistula
- Persistent post-surgical phrenic nerve paralysis at 12 months
- Severe pulmonary vein stenosis (>70%)

Table 3 summarized the primary safety endpoint definitions.

Table 3: Primary Safety Endpoint Definitions

able 3: Primary Safety Endpoint Definitions					
Potential Serious					
Adverse Event	Definition				
Cardiac Death	Excludes all non-cardiac deaths.				
Stroke	A new focal neurological deficit of presumed vascular origin persisting more than 24 hours and with a neuro-imaging study that does not indicate a different etiology. All patients suspected of having a stroke will be evaluated by a neurologist and have appropriate imaging tests performed (CT or MRI) as determined by a neurologist.				
	 The 24-hour criterion is excluded if the subject undergoes cerebrovascular surgery or dies during the first 24 hours. 				
	This stroke definition includes subjects presenting with clinical signs and symptoms suggestive of subarachnoid hemorrhage, intracerebral hemorrhage, or cerebral infarction.				
	Stroke events in cases of blood disorders such as leukemia, and strokes secondary to trauma are excluded.				
Transient Ischemic Attack (TIA)	A focal ischemic neurological deficit of abrupt onset and of presumed vascular etiology that resolves completely within 24 hours of onset. All patients suspected of having a TIA will be evaluated by a neurologist and have appropriate imaging tests performed (CT or MRI) as determined by a neurologist.				

Potential Serious Adverse Event	Definition
Myocardial Infarction* (MI)	The presence of any one of the following criteria: 1) detection of ECG changes indicative of new ischemia (new ST-T changes or new LBBB), which persist for more than one hour; 2) development of new pathological Q waves on an ECG; 3) imaging evidence of new loss of viable myocardium or new regional wall motion abnormality.
Excessive Bleeding*	Bleeding requiring re-operation or 2 units of PRBC transfusion within any 24 hours of the first 7 days following the index procedure.
Atrioesophageal Fistula	An atrial esophageal fistula is defined as a connection between the atrium and the lumen of the esophagus. Evidence supporting this diagnosis includes documentation of esophageal erosion combined with evidence of a fistulous connection to the atrium such as air emboli, an embolic event, or direct observation at the time of surgical repair. A CT scan or MRI scan are the most common methods of documentation of an atrial esophageal fistula.
Phrenic Nerve Paralysis*	Absent phrenic nerve function as assessed by a sniff test. A phrenic nerve paralysis is defined as permanent if it persists for 12 months or longer following ablation.
Pulmonary Vein Stenosis*	A reduction of the diameter of a PV or first generation PV branch. PV stenosis can be categorized as mild <50%, moderate 50%-70%, and severe ≥70% based on the percentage reduction in the diameter of the PV or PV branch. A severe PV stenosis should be considered a major complication of AF ablation.

^{* 2012} HRS/EHRA/ECAS Expert Consensus Statement on Catheter and Surgical Ablation of Atrial Fibrillation: Recommendations for Patient Selection, Procedural Techniques, Patient Management and Follow-up, Definitions, Endpoints, and Research Trial Design.

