5.13.3 Pre-Discharge

Prior to hospital discharge the following data will be collected:

- Use, changes in or discontinuation of anticoagulation, rate control and/or antiarrhythmic medications;
- Cardioversion(s) since surgery;
- For subjects on warfarin, assessment of INR therapeutic levels (maintain as clinically indicated);
- For subjects on dabigatran, perform a PTT and, if required, a thrombin time (Section 4.7.2.7 Anticoagulation Regimen);

- Cardiac rhythm as determined by a 12-lead ECG on day of hospital discharge;
- Heart failure status as assessed by NYHA classification on day of hospital discharge; and Adverse Events.

5.13.4 1 Month Follow-Up

Discharged subjects will return for an office visit 30 days (± 7 days) postablation treatment. Subjects that continue to be hospitalized 30 days postablation will have their 30-Day Follow-Up assessment performed at discharge. At a minimum, the following data will be collected at 30 Day Follow-Up visit:

- Use, changes in or discontinuation of anticoagulation, rate control and/or antiarrhythmic medications;
- Cardioversions since last visit;
- For subjects on anticoagulants, assessment of INR/PTT therapeutic levels (maintain as clinically indicated):
- Cardiac rhythm as determined by a 12-lead ECG at the time of the visit;
- Heart failure status as assessed by NYHA classification at the time of visit;
- Any hospital readmissions, including admission and discharge dates, since discharge from the original procedure; and

5.13.5 3 Month Follow-Up

Subjects will return for an office visit at the end of the blanking period (90 days \pm 14 days post-ablation treatment). During the blanking period, any recurrence of AF will be documented; however, recurrences of AF, AFL or AT during this time will not be considered therapeutic treatment failures. Subjects are not permitted to undergo repeat ablation during the blanking period. If a repeat ablation procedure is performed during this time, the subjects will be considered a therapeutic treatment failure and exited from the study.

At a minimum, the following data will be collected at the end of the blanking period follow-up visit:

- Use, changes in or discontinuation of anticoagulation, rate control and/or antiarrhythmic medications;
- Cardioversions since last visit;
- Any additional ablation procedures performed;
- For subjects on anticoagulants, assessment of INR/PTT therapeutic levels (maintain as clinically indicated);

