- Cardiac rhythm as determined by a 12-lead ECG at the time of the visit;
- Heart failure status as assessed by NYHA classification at the time of visit;
- Any hospital readmissions, including admission and discharge dates, since the previous visit; and
- Adverse events.
- If a subject is symptomatic for AF at the end of the blanking period, an event monitor will be provided to be used up to the 6-month follow-up visit to capture AF episodes.
- Patients will undergo an electro-anatomical remapping procedure to assess electrical isolation of the posterior left atrium and pulmonary veins. Any electrical gaps may be closed at the investigator's discretion using a commercially approved ablation device. This will consist of placement of catheters in the left atrium via femoral access and transeptal puncture using conventional electrophysiology techniques.
- Patients will undergo a cardiac CT or MRI scan at 3 months to assess the patency of the pulmonary veins.

5.13.6 6 Month Follow-up

Subjects will return for an office visit 6 months (180 days \pm 30 days) postablation treatment. At a minimum, the following data will be collected at 6 months:

- Use, changes in or discontinuation of anticoagulation, rate control and/or antiarrhythmic medications;
- Cardioversions since last visit;
- · Any additional ablation procedures performed;
- For subjects on anticoagulants, assessment of INR/PTT therapeutic levels (maintain as clinically indicated);
- Cardiac rhythm as determined by a 12-lead ECG at the time of the visit;
- Heart failure status as assessed by NYHA classification at the time of visit;
- Cardiac rhythm as determined by a 24-hour continuous ECG monitor following the visit for subjects in NSR at the time of the visit;
- Any hospital readmissions, including admission and discharge dates, since the previous visit; and
- Adverse events.

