5.13.7.2 Electro-anatomical mapping

The pre-ablation mapping will be performed using either the Rhythmia System and Orion Catheter (Boston Scientific, Natick Massachusetts USA) or the CARTO System and Penta-Ray Catheter (Biosense Webster, Diamond Bar California USA). These systems and their accessory devices (mapping catheters and ECG patches) bear a CE mark. The mapping procedure will begin with femoral venous access and introduction of a CE marked transseptal sheath and needle (e.g., Agilis, St. Jude Medical, St. Paul Minnesota USA) to gain access to the left atrium. The mapping catheter will be introduced and used to collect baseline electrograms (EGMs) and demonstrate electrical communication of the pulmonary veins to the left atrium. An electro-anatomical map will be created and the diagnostic catheters will be withdrawn. This same process will be before and after ablation.

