7.7 Assessment of Safety

7.7.1 Primary Safety Endpoint

A composite safety endpoint consisting of the proportion of subjects that experience one or more of the following serious adverse events (SAEs) related to the investigational procedure and/or device within 30 days of the PEF ablation procedure or hospital discharge, whichever is later, except as noted below:

- Cardiac death
- Stroke and/or transient ischemic attack (TIA)
- Myocardial infarction (MI)
- Excessive bleeding or
- Atrio-esophageal fistula
- Persistent post-surgical phrenic nerve paralysis at 12 months
- Severe pulmonary vein stenosis

All adverse events (AEs) will be adjudicated for seriousness as well as device and procedure relatedness.

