8.2 Adverse Event Reporting

All AEs, including all SAEs, will be monitored from the time of enrollment through discharge for this trial. All AEs must be recorded in the patient chart and Case Report Form (CRF). A description of the event, including the start date, resolution date, action taken and the outcome should be provided along with the Investigator's assessment of the relationship between the AE and the trial device.

All AEs should be followed until the event is resolved or judged to be chronically stable. The investigational site will provide relevant follow-up information to the Sponsor upon request.

The investigator should report to the Sponsor or its designee the following events, whether expected or not, in the corresponding sheet of the CRF, with the exception of AEs / SAEs detected before the patients has signed the patient consent form.

- AE
- SAF
- Device Deficiencies that did not but might have led to a SAE if:
 - Suitable action has not been taken or

- Intervention had not been made or
- If circumstances had been less fortunate
- New findings/updated in relation to already reported events.

If an AE / SAE is present at the beginning of study prior to the subject providing signed consent to participate in the study, only its worsening should be reported.

The investigator shall notify the sponsor and the CRO immediately and not later than 24 hours after the investigator has become aware of a SAE or device deficiency that might have led to a SAE via the Adverse Event Form of the CRF.

This reporting should be done by faxing completed CRF pages to the CRO:

CRO: MedPass International SAS

[contact]

Sponsor: FARAPULSE, Inc. [contact]

Email: [contact]
Contact: [name]

In the case of a SADE, when possible, the device involved in the failure or malfunction is to be returned to the Sponsor for analysis.

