10.12 Clinical Events Committee

A Clinical Events Committee (CEC) will convene during the study to classify and adjudicate all procedure-related and serious adverse events reported in this clinical study. The CEC will consist of physicians who have no formal involvement or conflict of interest with the subjects, the investigators, the designated CRO, and will be appointed by the Sponsor. The CEC will consist of three members with appropriate medical training and expertise in the fields of electrophysiology and cardiothoracic surgery. The CEC will be provided with case summaries and relevant source documents in order to adjudicate the adverse events. In addition to adverse event classification and adjudication, the CEC will have the authority to pause or terminate this investigation based on safety if, in its opinion, continuation is not in the best interests of the study subjects.

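### Severe pulmonary vein stenosis has no exception to the 30-day/discharge primary safety window, yet its only scheduled post-ablation scan falls on day 76 to 104 and no rule says how a finding there is dated or counted

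*Combined protocol and SAP*

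**What the plan says.** **Window.** The synopsis, 5.4.1 and 7.7.1 count SAEs related to the procedure or device "within 30 days of the PEF ablation procedure or hospital discharge, whichever is later, except as noted below". Among the components, only phrenic nerve paralysis has a later time (12 months). Table 3 also gives excessive bleeding its own, shorter period, the first 7 days.

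**Stenosis component.** The entry in 5.4.1 is "Severe pulmonary vein stenosis (>70" percent, and the synopsis has the same entry. Table 3 defines stenosis by reduction in vein diameter, with moderate as 50% to 70% and severe as 70% or more. 7.7.1 names the component without a cut-off. None of these places gives a time.

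**Imaging.** Cardiac CT/MRI appears in Table 4 at baseline and Month 3 only. 5.13.5 states its purpose: "Patients will undergo a cardiac CT or MRI scan at 3 months to assess the patency of the pulmonary veins". The Month 3 visit is at 90±14 days. Electro-anatomical maps are also made on the procedure day, but 5.13.7.2 says that the mapping catheter is used to "demonstrate electrical communication of the pulmonary veins to the left atrium", which is not a measurement of diameter.

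**Dating and adjudication.** 8.2 asks for event details: "A description of the event, including the start date, resolution date, action taken and the outcome should be provided". 7.7.1 says: "All adverse events (AEs) will be adjudicated for seriousness as well as device and procedure relatedness". 10.12 has the CEC "classify and adjudicate all procedure-related and serious adverse events reported in this clinical study". None of these says how to date an imaging finding whose onset is unknown.

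**The concern.** Under Table 3, stenosis is a measured reduction in diameter, so a subject without symptoms would be identified only by imaging. The one scan that the protocol schedules for this comes well after the stated window. A severe stenosis found there could be left out of the primary safety figure, or two analysts could count the same scan differently while each followed the text.

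Table 3 regards severe stenosis as a major complication, and 7.1 says that the results will inform the design of further studies. The primary composite is the safety figure that those designs are most likely to take up.

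**Working it through.** The plan has no power or sample-size figure to reproduce. The check is date arithmetic and a comparison of the sections.

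**Step 1. When the scan happens** (5.13.5, Table 4)
- Earliest: 90 − 14 = day 76. Latest: 90 + 14 = day 104.
- Distance beyond day 30: 76 − 30 = 46 days to 104 − 30 = 74 days.

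**Step 2. If the event is dated by detection**

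The window sentence can be read in two ways. The table shows the discharge day needed for a scan-detected case to count.

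| Scan day | Window ends at the later of day 30 and discharge | Window ends 30 days after discharge |
|---|---|---|
| 76 | day 76 or later | 76 − 30 = day 46 or later |
| 90 | day 90 or later | 90 − 30 = day 60 or later |
| 104 | day 104 or later | 104 − 30 = day 74 or later |

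On either reading, only a very long stay brings the scan inside the window. 5.13.4 says "Subjects that continue to be hospitalized 30 days postablation will have their 30-Day Follow-Up assessment performed at discharge", but that fixes the timing of a visit. It does not decide between the two readings of the endpoint.

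**Step 3. If the event is dated by onset**

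No CT/MRI is scheduled between the procedure and day 76. A stenosis absent at baseline and present at Month 3 may have arisen at any time between the ablation and the scan. Scheduled data cannot place it before or after day 30. The start date in 8.2 is a field to complete and does not say how to complete it.

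**Step 4. Effect of one omitted case**

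Take 25 subjects (the maximum in 5.5) and a case that is a related SAE in a subject with no other component event. Effect on the primary proportion: 1/25 = 0.040, or 4.0 percentage points.

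**Step 5. How likely such a case is**

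The documents do not say. 3.4 names PV stenosis among ablation complications without a rate, and Table 1 has no row for it. 3.3 cites porcine studies: one (N=10) found no stenosis at 3 weeks and another (N=6) confirmed this to 3 months. This is reassuring but too little to set a human rate.

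**Step 6. Cut-off at exactly 70%**
- Synopsis and 5.4.1: not severe, because the value must exceed 70%.
- Table 3: both moderate and severe.
- 7.7.1: no cut-off given.

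**The case against.** The strongest reply is that the plan has other routes for such a case.

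- **The CEC can decide.** It sees source documents and could assign an onset inside the window, and unscheduled imaging could find a case earlier. This stands as a possibility. It is why the text is best called ambiguous, and not certain to exclude. It still leaves the count to a judgement with no stated rule.
- **The exception phrase may have been meant to cover stenosis.** Perhaps, but no section says so.
- **The secondary safety endpoint would show it.** A case classed as an SAE would normally fall in the Day 30 to Month 3 interval, or in the next one if the scan follows the Month 3 visit. But that endpoint counts subjects with any SAE and does not identify stenosis. SAE status is also open for a silent finding: the limb of 8.1 on lasting damage to a body structure and the wording of Table 3 support it, but neither settles it.
- **The study is descriptive.** This stands. There is no hypothesis test or required sample size (7.1), and with at most 25 subjects any case can be described individually.

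A reader might infer a definite undercount and attach a probability to it. The documents do not support that. Such a figure would need an assumed stenosis rate, dating by detection, and every severe stenosis being a related SAE, and the plan establishes none of the three.

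**Conclusion.** The gap is real and should be fixed. A primary safety component has no time noted beyond 30 days or discharge, its only scheduled test falls on day 76 to 104, and no rule dates or counts what that test finds. The primary proportion can omit a scan-detected severe stenosis or vary with the reader.

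The size is 4.0 points per omitted case at n=25. This assumes that the case is a related SAE, that the subject has no other component event, and that the dating used puts it outside the window. The expected number of such cases is unknown.

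A reader might also infer that the visit-timing text in 5.13.4 makes the window end at discharge. It does not settle this, and the point holds on both readings. The inconsistent cut-off is minor, since it affects only a measurement of exactly 70%. No formal decision in this study depends on any of this.

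**What to change.** In the synopsis, 5.4.1 and 7.7.1:

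1. Add a noted exception such as: severe PV stenosis detected through the Month 3 CT/MRI. Keep the related-SAE basis of the composite, with CEC adjudication. Counting by detection up to that scan removes the need to guess an onset date.
2. List beside the primary result any severe stenosis on imaging that is not classed as an SAE. Such a case stays outside the composite even after change 1, so it should be visible.
3. Report the number of subjects scanned as the denominator for the stenosis component, since 7.4 uses available data without imputation.
4. Use one severity cut-off with non-overlapping categories, and carry it into Table 3 as well.

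The cost is protocol wording only, because the Month 3 scan is already required. The reported primary event rate may be slightly higher, and this component is complete only after the Month 3 scan. That does not delay the full composite, which the phrenic nerve component already keeps open to 12 months.
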